**APPENDIX II: CHADS2, CHA2DS2-VASc and HAS-BLED Scores**

The CHADS2 score was developed from five clinical parameters to identify non-valvular AF patients at an elevated risk for ischemic stroke. One point is added for patients who have the following: congestive heart failure, hypertension, age ≥ 75 years, and diabetes mellitus. Two points are given for patients with a prior stroke/TIA/thromboembolism. The CHADS2 score ranges from 0 to 6. A limitation of the CHADS2 score is that a subset of patients with a CHADS2 score of 1 may have other risk factors for embolic stroke. This limitation is overcome by the use of the CHA2DS2-VASc score, which is another ischemic stroke risk stratification method in subjects with non-valvular atrial fibrillation. The score assigns 1 or 2 points for each of the following risk factors: congestive heart failure, hypertension (defined as blood pressure consistently above 140/90), age ≥75 years, diabetes mellitus, prior stroke or TIA or thromboembolism, vascular disease, age 65 to 74 years, female gender. The score ranges from a minimum of 0 to a maximum of 9, with lower scores having lower risk and higher scores having higher risk for ischemic strokes. Subjects in the trial must have a minimum CHA2DS2-VASc score of 3 or a minimum CHADS2 score of 2.

CHADS 2		CHA 2 DS 2 -VASc	
Risk Factor	Points	Risk Factor	Points
Congestive Heart Failure	1	Congestive Heart Failure a	1
Hypertension	1	Hypertension	1
Age ≥ 75 years	1	Age > 75 years	2
Diabetes Mellitus	1	Diabetes Mellitus	1
Stroke/TIA/Thromboembolism	2	Stroke/TIA/Thromboembolism	2
		Vascular Disease (prior myocardial infarction, peripheral artery disease or aortic plaque)	1
		Age 65 to 74 years	1
		Female	1
Maximum Score	6	Maximum Score	9

a Heart failure with reduced ejection fraction or recent heart failure hospitalization (irrespective of ejection fraction)

	Title: The WAVECREST 2 Trial  Clinical Investigational Plan	Doc. #: CHX_IP014	Rev: H
---	--	-----------------------------	------------------

The HAS-BLED Score is one of the tools currently available to assess bleeding risk in AF subjects. The score assigns 1 point for the presence of each of the following: hypertension (uncontrolled systolic blood pressure > 160 mmHg), abnormal renal and/or liver function, previous stroke, bleeding tendency or predisposition, labile INRs, elderly and concomitant drugs and/or alcohol excess. The score ranges from 0 to 9, with scores  $\geq 3$  indicating high risk of bleeding. This score will be calculated for all subjects but will not be used to determine eligibility in the trial.

**Bleeding Risk Stratification with HAS-BLED Score**

Risk Factor	Points
Hypertension (systolic blood pressure > 160mmHg)	1
Abnormal renal and liver function* (1 point each)	1 or 2
Stroke	1
Bleeding tendency/predisposition*	1
Labile INRs (if on warfarin)*	1
Elderly (e.g., age > 65 years)	1
Medication predisposing to bleeding (antiplatelet, NSAID, etc.)	1
Drugs or alcohol (>8 drinks/week) (1 point each)*	1
Maximum Score	9

a Abnormal renal function is classified as the presence of chronic dialysis, renal transplantation, or serum creatinine  $\geq 200$  mmol/L. Abnormal liver function is defined as chronic hepatic disease (e.g., cirrhosis) or biochemical evidence of significant hepatic derangement (bilirubin 2 to 3 times the upper limit of normal, in association with aspartate aminotransferase/alanine aminotransferase/alkaline phosphatase 3 times the upper limit of normal, etc.), history of bleeding or predisposition (anemia), labile INR (i.e., time in therapeutic range < 60%), concomitant antiplatelets or nonsteroidal anti-inflammatory drugs, or excess alcohol.

	Title: The WAVECREST 2 Trial  Clinical Investigational Plan	Doc. #: CHX_IP014	Rev: H
---	--	-----------------------------	------------------

### APPENDIX III: Questionnaire for Verifying Stroke-Free Status (QVSFS)

This questionnaire has 8 questions, as follows. At study follow-up visits, these questions need to be preceded by “Since your last study visit...”:

1. Were you told by a physician that you had a stroke?  
 Yes  No
  
2. Were you told by a physician that you had a TIA, mini-stroke or transient ischemic attack?  
 Yes  No
  
3. Have you had a sudden painless weakness on one side of your body?  
 Yes  No
  
4. Have you had sudden numbness or a dead feeling on one side of your body?  
 Yes  No
  
5. Have you had sudden painless loss of vision in one or both eyes?  
 Yes  No
  
6. Have you suddenly lost one half of your vision?  
 Yes  No
  
7. Have you suddenly lost the ability to understand what people are saying?  
 Yes  No
  
8. Have you suddenly lost the ability to express yourself verbally or in writing?  
 Yes  No

QVSFS scores are obtained by giving 1 point to each “Yes” answer. The scores range from 0 (no questions positive) to 8 (all 8 questions positive).

	Title: The WAVECREST 2 Trial  Clinical Investigational Plan	Doc. #: CHX_IP014	Rev: H
--	--	-----------------------------	------------------

## APPENDIX IV: Neurologic Assessments

### Modified Rankin Scale

Refer to: [http://www.strokecenter.org/wp-content/uploads/2011/08/modified\\_rankin.pdf](http://www.strokecenter.org/wp-content/uploads/2011/08/modified_rankin.pdf)

### NIH Stroke Scale

Refer to: [https://stroke.nih.gov/documents/NIH\\_Stroke\\_Scale.pdf](https://stroke.nih.gov/documents/NIH_Stroke_Scale.pdf)

1.0 REVISION HISTORY

[REDACTED]	[REDACTED]	[REDACTED]	[REDACTED]
[REDACTED]	[REDACTED]	[REDACTED]	[REDACTED]
[REDACTED]	[REDACTED]	[REDACTED]	[REDACTED]
[REDACTED]	[REDACTED]	[REDACTED]	[REDACTED]

2.0 INTRODUCTION

This is the Statistical Analysis Plan (SAP) for the final analysis of data collected under Clinical Investigation Plan (CIP) CHX_IP014. This SAP describes in detail the statistical methodology and statistical analyses for the above-mentioned protocol.

2.1 Study Objectives

This trial is designed to demonstrate non-inferiority of the Coherex WaveCrest LAA occlusion device to the Boston Scientific Watchman LAA occlusion device for both effectiveness and safety endpoints.

- The primary effectiveness objective is to demonstrate non-inferiority of the WaveCrest device to the Watchman device for the composite rate of ischemic stroke or systemic embolism. If non-inferiority is demonstrated, superiority will be evaluated.
- The primary safety objective is to demonstrate non-inferiority of the WaveCrest device to the Watchman device for the composite rate of all death, procedure- and device-related complications requiring percutaneous or surgical intervention through 45 days post-procedure, and major bleeding throughout the duration of the trial. If non-inferiority is demonstrated, superiority will be evaluated.

[REDACTED]

- [REDACTED]

- [REDACTED]

2.2 Study Design Overview

The WAVECREST2 trial is a prospective, multicenter, randomized, active controlled, clinical trial to evaluate the effectiveness and safety of the Coherex WaveCrest LAA device compared to the Watchman® LAA device for the reduction in risk of ischemic stroke or systemic embolism in patients with non-valvular atrial fibrillation who have an appropriate rationale to seek a non-pharmacologic alternative to chronic oral anticoagulation.

Subjects will be randomized in a 1:1 ratio to the Treatment Arm (Coherex WaveCrest LAA Occlusion System) or the Control Arm (Boston Scientific’s Watchman LAA Device). The trial is designed to demonstrate that effectiveness and safety of the WaveCrest device are non-inferior to the Watchman device.

[REDACTED]

The enrollment phase is expected to last between 2 and 3 years, and maximum follow-up duration is 5 years, resulting in a total trial duration of up to approximately 8 years.

2.3 [REDACTED]

[REDACTED]

2.4 Data Monitoring Committee

The Data Monitoring Committee (DMC) will review accumulating data from the trial on a regular basis. The DMC will advise the Sponsor regarding the continuing safety of trial subjects and those yet to be recruited to the trial, as well as the continuing validity and scientific merit of the trial. Based on accumulating data from the trial, the DMC will recommend whether to continue, suspend, modify or stop the trial. The DMC will be composed of at a minimum one statistician and two physicians. The composition, responsibilities, frequency of DMC meetings, handling of emergency situations and documentation of DMC meetings will be specified in a Data Monitoring Committee Charter.

3.0 STUDY ENDPOINTS

3.1 Primary Endpoints

The primary safety endpoint is the composite rate of death, procedure- or device-related complications requiring percutaneous or surgical intervention, through 45 days post-procedure, and major bleeding throughout the duration of the trial.

The primary effectiveness endpoint is the composite rate of ischemic stroke or systemic embolism.

3.2 Secondary Endpoints

The first secondary effectiveness endpoint is the rate of ischemic stroke or systemic embolism with the WaveCrest device in comparison to the CHA₂DS₂-VASc imputed risk of ischemic stroke or systemic embolism in the absence of anticoagulant therapy.

The second secondary effectiveness endpoint is the percentage of subjects in the WaveCrest arm who have achieved effective LAA closure at 45 days (defined as having residual flow \leq 5 mm based on the 45-day TEE).

[REDACTED]

4.0 SUBJECT DISPOSITION

Subject disposition will be summarized with counts and percentages for each treatment group and in total. Categories summarized will include the number of subjects who signed informed consent, number of screen failures, and the number randomized, completed, and discontinued, as well as reasons for discontinuation. The summary of disposition will also include the number and percentage of subjects included in each analysis set described in Section 6 below.

5.0 ENROLLMENT AND ACCOUNTABILITY

The number and percentage of subjects completing each study visit will be summarized for all randomized subjects by randomized treatment group and in total. Following implantation, subject office visits are scheduled at 45 days, 6 months and annually through 5 years. Subjects are also scheduled to complete phone visits at 1.5, 2.5, 3.5, and 4.5 years after implantation.

[REDACTED]

6.1 [REDACTED]

[REDACTED]

6.2 [REDACTED]

[REDACTED]

6.3 [REDACTED]

[REDACTED]

- [REDACTED]
- [REDACTED]
- [REDACTED]
- [REDACTED]
- [REDACTED]
- [REDACTED]
- [REDACTED]
- [REDACTED]

[REDACTED]

6.5 Roll-in Subjects Cohort

This cohort will consist of all subjects identified as roll-in subjects per the CIP who had vascular access attempted.

6.6 As-Treated Cohort

This cohort will consist of all randomized subjects who received the LAA occlusion device independently of which treatment group they were randomized to.

7.0 GENERAL STATISTICAL CONSIDERATIONS

7.1 Summary Statistics

Subject data will be summarized using listings and tables. All critical electronic case report form (eCRF) data will be listed per subject for all enrolled subjects. All listings will include the subject number and the randomized treatment arm (or identification of roll-in subjects as appropriate). For continuous variables, descriptive statistics will include, at a minimum, the number of observations, mean, standard deviation, median, minimum, and maximum. For categorical variables, the number and percentage of subjects will be presented.

[Redacted]

7.2 [Redacted]

[Redacted]

[Redacted]

[Redacted]

7.3 [Redacted]

[Redacted]

[Redacted]

[REDACTED]

8.0 STATISTICAL METHODS

8.1 Demographics and Baseline Characteristics

A minimum of the following demographic and baseline characteristics will be summarized and compared between the WaveCrest and Watchman arms [REDACTED]

[REDACTED]

8.2 Primary Safety Endpoint

The primary safety endpoint is the composite rate of death, procedure- or device-related complications requiring percutaneous or surgical intervention, through 45 days post-procedure, and major bleeding throughout the duration of the trial.

The primary analysis of this endpoint for establishing trial success will occur in the ITT cohort and will apply Bayesian methods. [REDACTED]

[REDACTED].

Let $q_{\text{WAVECREST}}$ be the primary safety endpoint rate at 24 months in the WaveCrest arm, while q_{CONTROL} is the corresponding rate in the Watchman arm.

[REDACTED]

[REDACTED]

[REDACTED]

[figure not shown]
[REDACTED]

[Redacted text]

$$\frac{\sum_{i=1}^n \frac{q_{i, \text{WAVECREST}}}{q_{i, \text{CONTROL}}} + \sum_{i=1}^n \frac{q_{i, \text{CONTROL}}}{q_{i, \text{WAVECREST}}}{2n}$$

$$\frac{\sum_{i=1}^n \frac{q_{i, \text{WAVECREST}}}{q_{i, \text{CONTROL}}} + \sum_{i=1}^n \frac{q_{i, \text{CONTROL}}}{q_{i, \text{WAVECREST}}}{2n}$$

The following null and alternative hypotheses will be tested:

$$H_0: q_{\text{WAVECREST}}/q_{\text{CONTROL}} \geq 1.0 \text{ vs.} \\ H_a: q_{\text{WAVECREST}}/q_{\text{CONTROL}} < 1.0$$

8.2.1 Justification of the Non-inferiority Margin for the Safety Endpoint

Complications requiring percutaneous or surgical intervention through 45 days will likely consist of pericardial effusion/tamponade, vascular repair, and embolized device retrieval. The WaveCrest device has been designed to avoid the most serious of these complications, namely device embolization and life-threatening LAA perforations which may require surgery. These events are rare and while clinically important, are expected to contribute little to the composite endpoint.

[REDACTED]

8.3 Primary Effectiveness Endpoint

The primary effectiveness endpoint is the composite rate of ischemic stroke or systemic embolism.

[REDACTED]

Let $p_{\text{WAVECREST}}$ be the primary effectiveness endpoint rate at 24 months in the device arm, while p_{CONTROL} is the corresponding rate in the control arm.

[REDACTED]

[REDACTED]
[REDACTED]
[REDACTED]
[REDACTED]
[REDACTED]

[REDACTED]

[Redacted text block]

[Redacted]	}	[Redacted]	[Redacted]	}	[Redacted]
		[Redacted]	[Redacted]		[Redacted]
		[Redacted]	[Redacted]		[Redacted]
		[Redacted]	[Redacted]		[Redacted]
		[Redacted]	[Redacted]		[Redacted]
		[Redacted]	[Redacted]		[Redacted]

[Large redacted text block]

[Redacted text block]

[REDACTED]

[REDACTED]

[REDACTED]

If non-inferiority is established for both the primary safety, the primary effectiveness endpoints and the second secondary effectiveness endpoint, the primary safety endpoint will then be tested for superiority, and if superiority is established for the primary safety endpoint, then the primary effectiveness endpoint will be tested for superiority. The following null and alternative hypotheses will be tested:

$$H_0: p_{\text{WAVECREST}} - p_{\text{CONTROL}} \geq 0.0\%$$

$$H_a: p_{\text{WAVECREST}} - p_{\text{CONTROL}} < 0.0\%$$

8.3.1 Justification of the Non-inferiority Margin for the Effectiveness Endpoint

By demonstrating statistical non-inferiority to Watchman, the WAVECREST2 Trial is designed to make the WaveCrest device available as an additional alternative to oral anticoagulation for patients with a reason to seek a non-pharmacologic alternative to chronic oral anticoagulation.

8.4 Secondary Effectiveness Endpoints

The first secondary effectiveness objective is to establish non-inferiority of the rate of LAA closure at 45 days for the WaveCrest arm compared to the control arm. Let $r_{\text{WAVECREST}}$ be the 45-day LAA closure rate in the device arm, while r_{CONTROL} is the corresponding rate in the control arm.

$$H_0: r_{\text{WAVECREST}} - r_{\text{CONTROL}} \geq 6.0\% \text{ vs.}$$

$$H_a: r_{\text{WAVECREST}} - r_{\text{CONTROL}} < 6.0\%.$$

The rate will be calculated as the number of subjects who have residual flow ≤ 5 mm based on the 45-day TEE divided by the number of subjects in each group with a 45-day TEE.

$$H_0: I_w \geq 6.0$$

$$H_1: I_w < 6.0$$

where I_w is the true rate of ischemic stroke or systemic embolism per 100 patient-years for the WaveCrest device. [REDACTED]

[REDACTED]

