## 15. STATISTICAL METHODS

This section summarizes the statistical methods for the WAVECREST 2 clinical trial. A detailed statistical analysis plan describing the sample size calculations and detailed statistical methods that will be applied to the data collected in this trial will be contained in a separate document entitled **Statistical Analysis Plan** which supersedes this summary. This document will be finalized prior to un-blinding of the database and any analysis of the data

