### 15.5 Secondary Effectiveness Endpoints

The first secondary effectiveness objective is to establish non-inferiority of the rate of LAA closure at 45 days for the WaveCrest arm compared to the control arm. The rate will be calculated as the number of subjects who have residual flow  $\leq 5$  mm based on the 45-day TEE divided by the number of subjects in each group with a 45-day TEE. Let  $I_{\text{WAVECREST}}$  be the 45-day LAA closure rate in the device arm, while  $I_{\text{CONTROL}}$  is the corresponding rate in the control arm. Specifically, the following null and alternative hypotheses will be tested:

$$H_0: I_{\text{WAVECREST}} - I_{\text{CONTROL}} \geq 8.0\% \text{ vs.}$$

$$H_a: I_{\text{WAVECREST}} - I_{\text{CONTROL}} < 8.0\%.$$

	Title: The WAVECREST 2 Trial  Clinical Investigational Plan	Doc. #: CHX_IP014	Rev: H
---	--	-----------------------------	------------------

The other secondary effectiveness objective is to demonstrate reduction in risk of ischemic stroke or systemic embolism with the WaveCrest device in comparison to the CHADS2 and CHA2DS2-VASc imputed risk of ischemic stroke or systemic thromboembolism in the absence of anticoagulant therapy.

The rate of ischemic stroke in subjects receiving the WaveCrest device in the Treatment Arm will be tested against a performance goal. The hypotheses to be tested are as follows:

$$H_0: I_w \geq 6.0$$

$$H_1: I_w < 6.0$$

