8.5 Sample Size and Power

A minimum sample size of 1250 subjects will be randomized in the trial up to a maximum of 1550 randomized subjects.

[REDACTED]

[REDACTED]

- [REDACTED]
- [REDACTED]
- [REDACTED]
- [REDACTED]

[REDACTED]

[figure not shown]
[Redacted text block]

[Redacted text block]

[Redacted text block]

[Redacted text block]

[Large redacted text block]

[Redacted text block]

[Large redacted text block]

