8.6 Multiplicity Adjustment

The trial will be considered successful if both the primary effectiveness and primary safety endpoints are met. [Redacted]

[Redacted text block]

[REDACTED]

[REDACTED]

[REDACTED]

[REDACTED]

[REDACTED]

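### The printed 45-day LAA closure hypotheses are reversed for a favourable outcome in both documents, so as printed a device with much lower closure passes as non-inferior; the margins also differ (8.0% v 6.0%)

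*SAP*

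**What the plan says.** SAP 8.4 gives the aim in words: "The first secondary effectiveness objective is to establish non-inferiority of the rate of LAA closure at 45 days", WaveCrest against control. Closure means residual flow of 5 mm or less on the 45-day TEE, so a higher rate is better. The null printed beneath is "r_{\text{WAVECREST}} - r_{\text{CONTROL}} \geq 6.0" percent, and the alternative is a difference below 6.0%.

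Protocol 15.5 states the same aim and endpoint, but its null is "I_{\text{WAVECREST}} - I_{\text{CONTROL}} \geq 8.0" percent, with the alternative below 8.0%. Protocol section 15 says of the SAP, "which supersedes this summary", so 6.0% formally governs.

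The numbering is not stable. SAP 3.2 says: "The second secondary effectiveness endpoint is the percentage of subjects in the WaveCrest arm who have achieved effective LAA closure at 45 days". SAP 8.4 calls closure the first secondary and makes it a two-arm comparison. SAP 8.3 requires non-inferiority on both primaries and on one secondary before any superiority test, and identifies that secondary only by number: "the second secondary effectiveness endpoint, the primary safety endpoint will then be tested for superiority".

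SAP 8.6 defines overall success without closure: "The trial will be considered successful if both the primary effectiveness and primary safety endpoints are met".

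**The concern.** For a favourable outcome, non-inferiority has to rule out a closure rate that is lower than control by the margin or more. The printed null instead says that WaveCrest is better by at least the margin, and rejecting it shows only that WaveCrest is not that much better. This form suits a harmful event, where a lower rate is good. Applied literally, the rule accepts a device with clearly lower closure and usually fails one that is better by about the margin or more.

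The direct harm is a false secondary claim. There may be a second one. If closure is the unnamed secondary in SAP 8.3, a reversed rule could wrongly open or block the superiority tests of the primaries. The margin conflict adds a choice that should not remain open once data are seen.

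**Working it through.** **Algebra.** Let d = rW − rC, the difference in true closure rates, and let m > 0 be the margin.

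- Printed: H0: d ≥ +m against Ha: d < +m. Every device with lower closure lies in Ha.
- Non-inferiority for a favourable rate: H0: d ≤ −m against Ha: d > −m.
- A lost minus sign does not explain the printed form. H0: d ≥ −m against Ha: d < −m would reward only a device worse by more than m.
- Swapped subscripts could explain it. H0: rC − rW ≥ m against Ha: rC − rW < m is the correct test written differently.

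**Inputs.** The visible text gives no test, alpha or planning closure rate for this endpoint, so there is no stated figure to reproduce. Sample size comes from SAP 8.5: "A minimum sample size of 1250 subjects will be randomized in the trial up to a maximum of 1550 randomized subjects". At 1:1 that is 1250/2 = 625 to 1550/2 = 775 per arm. The rest is assumed: one-sided 2.5%, an unpooled normal test, control closure of 85–95%, and 500 per arm as a low case (20% of 625 without a TEE). The only 45-day rate at the 5 mm threshold in the documents is 100%, from an earlier single-arm WaveCrest cohort (protocol 2.7).

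**Formulas.** se = √{[rW(1 − rW) + rC(1 − rC)]/n}

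- Printed test: P(pass) = Φ((m − d)/se − 1.96)
- Corrected test: P(pass) = Φ((m + d)/se − 1.96)

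**Worked case: control 90%, n = 625 per arm, m = 6%**

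| True d | se | Printed: z, P(pass) | Corrected: z, P(pass) |
|---|---|---|---|
| −12 points | 0.02046 | 6.84, >99.9% | −4.89, <0.1% |
| −6 points | 0.01895 | 4.37, >99.9% | −1.96, 2.5% |
| 0 | 0.01697 | 1.58, 94% | 1.58, 94% |
| +3 points | 0.01575 | −0.06, 48% | 3.75, >99.9% |
| +6 points | 0.01433 | −1.96, 2.5% | 6.41, >99.9% |

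A simulation of 400,000 runs for this case gave printed pass rates of 100.0% at −6, 48.1% at +3 and 2.8% at +6. The lost-minus-sign form passes 83% at −12 and about 0% at equality.

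**Range over control 85–95% and n = 500–775 per arm**

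| Truth | Printed, m = 6% | Printed, m = 8% | Corrected |
|---|---|---|---|
| 12 points worse | >99.9% | >99.9% | <0.1% at either margin |
| 6 points worse | ≥99.8% | ≥99.8% | 2.5% at 6%; 13–31% at 8% |
| Equal | 76–100% | 94–100% | same as printed |
| 3 points better | 28–90% | 64–100% | ≥98.6% |
| Better by exactly m | 2.5% | 2.5% | about 100% |
| 97% v 90% | 0.3–0.5% | 9–12% | about 100% |

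The lowest printed pass rate at 6 points worse occurs at control 85%, n = 500, m = 6%: se = 0.02422, z = 0.12/0.02422 − 1.96 = 2.99, giving 99.86%. An advantage larger than the margin is impossible once control closure exceeds 100 − 6 = 94% (6% margin) or 100 − 8 = 92% (8% margin).

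**Margin.** With the corrected test, control 95%, n = 625 and a true 3-point deficit, se = 0.01392. At 6%, z = 0.03/0.01392 − 1.96 = 0.20, power 58%. At 8%, z = 0.05/0.01392 − 1.96 = 1.63, power 95%.

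**The case against.** The stated aim is correct in words in both documents, and a statistician faced with much lower WaveCrest closure would probably not report non-inferiority. The slip may be no more than a reversed order of terms. Much of SAP 8.3 to 8.6 is redacted, so a correct decision rule may exist out of sight. The SAP supersedes the protocol summary, which settles the margin formally. Closure plays no part in trial success. Its role as a gate is an inference: SAP 8.4 numbers it first, and neither protocol 4.3.1 nor SAP 2.1 mentions a closure condition. A redacted block follows the SAP 3.2 text, so the one-arm wording there may be incomplete.

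Most of this stands as a limit on the consequence, and the percentages above describe the rule as printed, not a known procedure. None of it makes the printed hypotheses right. They are the only visible specification of the test, both documents have the same direction, and a correct hidden rule would contradict them. The term-order explanation leads to the same corrected hypotheses.

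**Conclusion.** The concern holds, and the hypotheses must be corrected. Both documents print a closure test in the wrong direction. That conclusion is algebraic and does not depend on alpha, sample size or the control rate; only the pass rates rest on the stated assumptions. The margins of 8.0% and 6.0% conflict, and the choice matters once the direction is right.

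The primary endpoints and the definition of trial success are not affected. SAP 3.2's numbering, and the word non-inferiority in SAP 8.3, suggest that closure is the gate to superiority testing, since the other secondary is tested against a fixed rate of 6.0 per 100 patient-years. The visible text does not settle this. Even if closure is the gate, each superiority test still has to reject its own null.

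**What to change.** - In SAP 8.4 and protocol 15.5, print H0: rW − rC ≤ −m against Ha: rW − rC > −m, where rW and rC are the WaveCrest and control closure rates.
- Use one margin in both documents: the SAP's 6.0%, unless the sponsor justifies another before unblinding.
- In SAP 8.3, name the secondary endpoint that gates superiority testing instead of citing it by number.
- Give closure one number throughout, and align the definition in SAP 3.2 with the two-arm comparison in SAP 8.4.
- Check that any redacted decision rule agrees with the corrected hypotheses.

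The cost is a wording change in the SAP and the protocol, with no new data. It should be made before unblinding, because a change of direction or margin after results are known could be challenged as post hoc.
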